1.0. Background

Childhood obesity is becoming a more severe problem in the United States, particularly in the southeast region of the nation. Maternal behaviors and characteristics are critical for determining the health of their children during the first few years of life. There is keen interest in better understanding factors associated with childhood obesity and potential interventions to lower its risk. In particular, there is interest in understanding the relative contribution of a mother's weight before, during, and after pregnancy on childhood obesity.

The Vanderbilt University Medical Center (VUMC) includes electronic medical records data for over 2 million patients. Linked data from mothers and children delivered at VUMC are available and provide us with the opportunity to study factors associated with childhood obesity from a large and diverse group of mothers and children. There are also some challenges with using electronic health records data for medical research, because the data are often more prone to errors. We will validate targeted subsamples of electronic health records and apply novel statistical methods to improve estimation.

2.0. Study Objective:

This study will examine the relative contributions of maternal weight trajectory before, during, and after pregnancy on the cumulative probability of childhood obesity at ages 2 and 5 years. We will consider whether patterns in mother weight, such as being overweight or obese before the pregnancy, gaining excess weight during pregnancy and not losing it, gaining excess weight during pregnancy and losing it, or not gaining excess weight affect the risk of childhood obesity. Other childhood outcomes in relation to obesity of the child and mother will also be considered, such as asthma and cardiovascular outcomes (e.g. high blood pressure).

2.1. Inclusion Criteria:

Mothers and child dyads at VUMC will be included. VUMC has the ability to link mother-child EHR, and in an earlier dataset, there were 27,390 mother-child pairs with an existing linkage recorded in a Mom-Baby Linkage table.

Maternal inclusion criteria:

- In a mother-child dyad in the Mom-Baby Linkage table
- Age ≥ 16 years
- At least one measure of weight within 273 days prior to birth of the baby

- At least one height measure

Child inclusion criteria:

- In a mother-child dyad
- At least 2 weights, where one weight occurs within 24 hours of birth
- At least one simultaneous height and weight measure at >730 days after birth and before 6 years of age

3.0. Outcomes

Primary outcome:

Time from birth to body mass index (BMI) at or above the 95th percentile based on sex-specific reference populations using CDC BMI-for-age growth charts for children ≤5 years

Secondary Outcomes:

- Child Weight at 2 years and 5 years
- Incidence of childhood obesity at 2 and 5 years
- Asthma at age 4-5 years

Exploratory outcomes:

Childhood comorbidities, including high cholesterol, and high blood pressure, in first five years of age

4.0. Study Design

This is a retrospective, observational study using already collected data. All eligible mother-child dyads in the VUMC Mom-Baby Linkage table will be included for study. We will be prospectively validating EHR data for a subsample of patient records from this cohort, further details are provided below.

5.0. Statistical Considerations

5.1. Analysis Considerations

Key covariates: Maternal race/ethnicity, maternal age at pregnancy event, maternal diabetes, tobacco use, medications, mode of delivery, maternal mental health status, socio-economic status, parity, marital status, alcohol use, child sex, child clinical diagnoses, and estimated gestational age of the child at delivery.

Proposed analyses: The cumulative probability of childhood obesity according to age will be estimated using Kaplan-Meier methods. Follow-up for primary time-to-event analyses will be the time from turning 2 years old until the first of childhood obesity, last measurement in the EHR, or 6 years. The association between time-to-obesity and maternal weight trajectories

before, during, and after pregnancy will be examined using Cox regression adjusted for the key covariates listed above. Maternal weight trajectories will be summarized using weight during the year prior to pregnancy, weight change during pregnancy, and weight change during the year after pregnancy. Weight change will be treated as a continuous variable for all analyses, although we may consider additional analyses that categorize it.

We anticipate substantial variation in the frequency of measurements across mothers and children, and we anticipate the appropriate choice of analysis method will depend on the level of completeness of the data. We may consider joint models of longitudinal maternal weight measurements and times-to-childhood obesity. We will also consider functional analysis methods to model overall trends in addition to individual weight trajectories. We will consider very carefully methods to adjust for potential biases that could arise if the numbers of measurements on a woman or child are informative of health status. We will consider propensity score type adjustments, to adjust for the propensity of having data at a specific milestone (e.g. child 2yr or 5yr birthday), as well as methods such as outputation (Follmann et al 2003) which will equalize the number of measures per individual to explore robustness of results across different methods to adjust for these potential biases. Standard methods, e.g. multiple imputation, will be used to handle missing data.

We will assess the association between maternal weight trajectories and childhood asthma at age 4 or 5 using logistic regression, limited to the children with data at ages 4 or 5 years. Multivariable logistic regression models will adjust for similar covariates to those described above for the obesity analyses.

Methods to address error in variables: We anticipate there being a moderate number of errors in weight measurements, primarily due to measurement error, but some also due to recording errors. We anticipate that date of birth will be largely accurate in the EHR, but that other dates and clinical events will be prone to errors. Some of the covariates (specifically, race, diabetes, tobacco use, and medications) are known to be particularly error-prone, and we anticipate that patient records with errors in one variable will tend to be more likely to have errors in multiple variables. We also anticipate a moderate number of errors in the linkage of maternal-child records.

We will implement a multi-wave, targeted validation sub-study; the validation strategy is outlined in the next section. Once we have obtained validation data for a subsample of patient records, we will perform the proposed study analyses highlighted above but augmented using specific methods to incorporate both the validated and unvalidated data. We will consider multiple analysis approaches as what is optimal for the problem may depend on the error structure. Namely, we will consider a maximum likelihood, multiple imputation, and generalized raking approaches. The optimal raking variable will be constructed using multiple imputation, as described in Han et al. (2019). Single imputation methods, such as regression calibration, in combination with raking will also be considered (Oh et al., 2019) These methods will take into account the targeted nature of the validation sample (i.e., the fact that the

validation sample is not a completely random sample, but rather a targeted random sample [e.g., weighted or stratified sampling] in the first and second validation waves).

Data Validation Strategy

Our goal will be to optimize the information learned (i.e., minimize variance of corrected estimates) based on our budgetary constraints; we anticipate we will be able to validate between 500-1000 records.

Data validators will receive validation training from Drs. [name], [name], and [name], and will enter validation data into standardized REDCap validation forms built off of the PCORnet Common Data Model. We anticipate validation that will happen in 2 waves. The first wave will be treated as a pilot sample and information learned regarding data discrepancies will be used to tailor the individuals selected in the second validation wave.

We will design our multi-wave validation sampling with two separate analyses in mind: (1) association between maternal weight change during pregnancy and time to childhood obesity and (2) association between maternal weight change during pregnancy and probability of asthma for child. We will design our validation sample such that we develop two separate sampling schemes to optimize these two separate analyses. As childhood obesity is our primary endpoint, approximately 2/3 of our chart reviews will be targeted towards this endpoint, the other 1/3 will be targeted towards childhood asthma. Naturally, the charts that are targeted for validation to improve estimation of the childhood obesity outcome will still be used for the childhood asthma analyses and vice versa, even though they are not targeted for that purpose.

For the first wave of validation sampling, no more than half of the records will be sampled according a balanced stratified sample, with randomly selected samples within strata. For the childhood obesity endpoint, we will create 6 strata based on all combinations of obesity (yes/no) and rate of maternal weight gain ($\leq 25^{\text{th}}$ percentile, $25^{\text{th}}\text{-}75^{\text{th}}$ percentile, $>75^{\text{th}}$ percentile). In wave 1 of chart validation, we will validate 40 charts per stratum (total of 240 charts). For the asthma endpoint, we will create 6 strata based on all combinations of childhood asthma (yes/no) and rate of maternal weight gain ($\leq 25^{\text{th}}$ percentile, $25^{\text{th}}\text{-}75^{\text{th}}$ percentile, $>75^{\text{th}}$ percentile); note that the only patients included in these analyses will be those children followed with at least one visit from ages 4-5 years. In wave 1, we will validate 25 charts per stratum (total of 150). Therefore, our first wave of chart reviews will include a total of 390 charts. For the chosen records, validation will be performed by going through the entire EHR (free text and other fields not part of the PCORnet Common Data Model) to validate key study variables, which include the primary outcomes, exposures, and key covariates given above. De-identified validation data will be securely transferred to study investigators (Drs. [name] and [name]) who will then use this information to tailor a second wave of data validation.

For the second wave of validation, we anticipate over-sampling/targeting records that are more influential, such as those that appear to be more prone to errors (based on our initial wave of data validation), records that are more likely to have observed events, and records with extreme values or influence on the estimating equations. We plan to target our samples to

minimize the variance of the estimate of our primary outcome (time-to-obesity) and secondary outcome (incidence of asthma). Hence, we plan to sample following adaptations of the mean-score sampling approach of McIsaac and Cook (2015) to optimize sampling for the discrete proportional hazards and logistic regression models. Neyman allocation strategies will be employed to assure efficiency and to guarantee sufficient information per stratum so that all analysis methods may be employed. If the first wave reveals a large amount of outcome misclassification, then these methods may be adjusted so as stratify on predicted true positive versus predicted true negative results, versus the error prone outcome alone in the second wave. For example, rather than sampling based on influence functions plugging in the phase 1 data, we may sample based on influence functions plugging in multiply imputation estimators based on the wave 1 validation. We anticipate validating several hundred additional records for this wave 2 validation; hopefully at least as many as in the wave 1 validation. Exact numbers to validate will be determined based on feasibility and costs learned from the wave 1 validation. Data from this second wave of validation will be similarly entered into REDCap and transferred to study investigators.

References

Han K, [name] PA, Lumley T. Combining multiple imputation with raking of weights in the setting of nearly-true models. (arXiv:1910.01162[stat.ME])

Oh E, [name] BE, Lumley T, [name] PA. Raking and Regression Calibration: Methods to Address Bias from Correlated Covariate and Time-to-Event Error. (arXiv:1905.08330v1 [stat.ME])

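### The child's year of birth is not among the key covariates, although the plan describes worsening childhood obesity and pools all linked births, so calendar time may confound the maternal weight association.

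*Combined protocol and SAP*

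**What the plan says.** The adjustment set is given once, in section 5.1. It opens with "Key covariates: Maternal race/ethnicity, maternal age at pregnancy event, maternal diabetes, tobacco use, medications, mode of delivery, maternal mental health status, socio-economic status" and closes with "parity, marital status, alcohol use, child sex, child clinical diagnoses, and estimated gestational age of the child at delivery". That makes 14 items, and none is year of birth, calendar period or year of delivery.

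The models refer back to that list. The association between maternal weight trajectory and time to obesity "will be examined using Cox regression adjusted for the key covariates listed above". For asthma, "Multivariable logistic regression models will adjust for similar covariates to those described above for the obesity analyses".

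Three other statements bear on the point:

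- Section 1.0: "Childhood obesity is becoming a more severe problem in the United States, particularly in the southeast region of the nation".
- Section 4.0: "All eligible mother-child dyads in the VUMC Mom-Baby Linkage table will be included for study". No range of birth years and no data cut-off date is given.
- Section 5.1, on errors in variables: "We anticipate that date of birth will be largely accurate in the EHR".

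Primary follow-up starts at age 2 and ends at obesity, the last EHR measurement or age 6 (section 5.1). One paired height and weight after day 730 and before age 6 meets the child's follow-up criterion (section 2.1), so short follow-up is allowed. Section 5.1 says that propensity-type adjustment for having data at a milestone will be considered. It names no predictors for that model.

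**The concern.** In a cohort pooled over an unstated span of births, calendar time is a candidate common cause. If the outcome becomes more frequent over the accrual period and mothers also become heavier, part of the period effect is credited to maternal weight. Maternal age, the only covariate close to a date, does not stand in for it. The CDC reference in section 3.0 is specific to age and sex and does not remove a calendar trend. The plan itself supplies half of the condition, a worsening outcome. It says nothing about the other half, a drift in maternal weight.

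A second and separate issue concerns the Kaplan-Meier estimate. A child under 6 at extraction must be censored early, so birth year bounds follow-up. If birth year also predicts obesity, censoring depends on an omitted predictor, and the age-5 estimate describes earlier births more than later ones. Cumulative probability at age 5 is part of the study objective (section 2.0).

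**Working it through.** The documents give no effect size, event count, birth-year range or trend, so there is no plan figure to reproduce. The omission itself is established by reading: no model, stratification, restriction or sensitivity analysis names birth year. Every number below rests on assumed inputs.

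**1. Possible bias in the HR for pre-pregnancy weight**

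Assumptions: births uniform over *n* = 8-12 years; log hazard of recorded obesity rising by *g* = 0.03-0.10 per birth year; maternal weight rising by *d* = 0.2-0.5 kg per year; weight SD 18 kg (variance 324); true log HR 0.015 per kg.

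First-order omitted-variable formula: bias per kg = *g* × *d* × Var(Y) / (324 + *d*² × Var(Y)), with Var(Y) = *n*²/12.

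| Case | *n* | *g* | *d* | Var(Y) | Bias per kg | Share of 0.015 | HR per 18 kg (true 1.310) |
|---|---|---|---|---|---|---|---|
| Low | 8 | 0.03 | 0.2 | 5.33 | 0.00010 | 0.7% | 1.312 |
| Middle | 10 | 0.05 | 0.3 | 8.33 | 0.00038 | 2.6% | 1.319 |
| High | 12 | 0.10 | 0.5 | 12.0 | 0.00183 | 12% | 1.354 |

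The true HR per 18 kg is exp(18 × 0.015) = 1.310. In the high case it becomes exp(18 × 0.01683) = 1.354. With *d* = 0 the bias is zero whatever *g* is.

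**2. Check by simulated Cox model**

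Assumptions: true HR 1.20 per SD of weight, a 15-year window, hazard ratio 1.05 per birth year, and administrative censoring that depends on birth year. Rho is the correlation of maternal weight with birth year.

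| Rho | HR, birth year omitted | HR, birth year included |
|---|---|---|
| 0 | 1.195 | 1.195 |
| 0.1 | 1.222 | 1.204 |
| 0.3 | 1.268 | 1.202 |

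At rho = 0.1 the excess is (ln 1.222 − ln 1.204) / ln 1.204, about 8% of the log HR. At rho = 0, censoring by birth year leaves the HR unchanged even with a marked outcome trend. The inputs in step 1 imply rho of about 0.03 to 0.10, so the rho = 0.3 row lies well outside them.

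**3. Pooled Kaplan-Meier estimate at age 5**

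Assumptions: births uniform over *n* years ending 2 years before cut-off; hazard from age 2 of *h*(y) = 0.06 × exp[*g*(y − *n*/2)] per year; no other censoring. A child born at time y can be followed for *n* − y years past age 2, so births in the last 3 years of the window cannot reach age 5 under observation.

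True risk = average over y of 1 − exp(−3*h*(y)). Pooled Kaplan-Meier limit = 1 − exp(−∫₀³ m(t) dt), where m(t) is the mean hazard among children still at risk and observable at t years past age 2.

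| *n* | *g* | True risk | Pooled Kaplan-Meier | Relative error |
|---|---|---|---|---|
| 8 | 0.03 | 16.5% | 16.2% | −2% |
| 12 | 0.03 | 16.5% | 16.2% | −2% |
| 8 | 0.10 | 16.8% | 15.6% | −7% |
| 12 | 0.10 | 17.2% | 16.0% | −7% |

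This error needs no drift in maternal weight. It needs only an outcome trend and some children under 6 at extraction.

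**The case against.** A reader might infer from the text that calendar trend does confound the maternal weight effect. The documents do not support that. Section 1.0 gives one qualitative sentence about the nation and the region, with no rate and nothing specific to this centre. Nothing says that maternal weight, weight change, asthma or EHR capture shifts with birth year. Only possible confounding of unknown size is supported.

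A reader might also infer that shorter follow-up for later births biases the HR. By itself it does not, as the rho = 0 simulation shows. The plan gives no birth range or cut-off, so even the presence of children under 6 at extraction is an inference, though a reasonable one.

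The size can fairly be called small. The 12% figure sets every input at its extreme, and a 10% yearly rise over 12 years is about a threefold rise in hazard (1.10¹² ≈ 3.1). The rho = 0.3 scenario would need maternal weight to rise about 0.3 × 18 / (15/√12) ≈ 1.25 kg per year, nearly 19 kg in all, and should carry no weight here. The formula omits the other covariates, some of which may absorb part of any drift. It also covers only pre-pregnancy weight. Weight change during pregnancy, the exposure that both validation designs target, has no estimate, and neither does asthma.

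Finally, the milestone propensity adjustment and the looser wording for the asthma covariates leave room for birth year. Both are tentative and neither names it. The propensity adjustment concerns data availability, not a common cause of exposure and outcome, and the asthma wording does not reach the Cox model, whose set is fixed by the list.

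These limits on size and certainty stand. They do not remove the omission.

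**Conclusion.** The point holds in a conditional form. The listed adjustment set lacks year of birth, while the plan describes a worsening outcome and pools births without a date limit. Calendar time **may** confound the maternal weight association. Under the assumed trends the bias is roughly 1-12% of the pre-pregnancy weight log HR, a few percent at mid-range inputs, and nil without a drift in maternal weight. For weight change and for asthma the size is not known.

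The Kaplan-Meier issue is separate and also conditional. With children under 6 at extraction and an assumed hazard trend of 3-10% per birth year, the pooled age-5 risk would be about 2-7% too low in relative terms, through dependent censoring.

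Neither effect is shown to be large. The case for acting is that the adjustment is specific, costs almost nothing, and uses a baseline variable that the plan already holds and expects to be largely accurate.

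**What to change.** - Add child year of birth, as a restricted cubic spline or in 2-year bands, to the key covariates in section 5.1, so that it enters the Cox model and, by name, the asthma logistic model.
- Include it in the imputation and raking models, and in any propensity model for having data at a milestone.
- Report the Kaplan-Meier curve by birth period, or standardised over birth period.
- State the range of birth years and the data cut-off date, so that a reader can see how many children could not have been followed to age 5 or 6.

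The cost is a few sentences in the SAP and a few degrees of freedom. No new data are needed, because date of birth is already required to compute the child's age.

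### The pre-pregnancy exposure is plain weight with no maternal height or BMI in the model, so it partly measures stature and cannot by itself identify mothers who were overweight or obese

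*Combined protocol and SAP*

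**What the plan says.** Section 2.0 sets out to compare the contributions of maternal weight before, during and after pregnancy. Among the patterns it will consider is "being overweight or obese before the pregnancy". The maternal criteria in section 2.1 include "At least one height measure", with no time window.

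Section 5.1 then defines the exposure: "Maternal weight trajectories will be summarized using weight during the year prior to pregnancy, weight change during pregnancy", followed by weight change in the year after. The Cox model adjusts for a list of fourteen items that begins "Key covariates: Maternal race/ethnicity, maternal age at pregnancy event, maternal diabetes, tobacco use, medications, mode of delivery". The rest of the list covers mental health, socio-economic status, parity, marital status, alcohol use, child sex, child diagnoses and gestational age. Neither maternal height nor maternal BMI is on it. On categorisation the section says "Weight change will be treated as a continuous variable for all analyses, although we may consider additional analyses that categorize it".

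For asthma, "Multivariable logistic regression models will adjust for similar covariates to those described above for the obesity analyses". Under Data Validation Strategy, chart review is to "validate key study variables, which include the primary outcomes, exposures, and key covariates given above". BMI appears explicitly only in the child outcome in section 3.0.

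**The concern.** Overweight and obesity are defined by weight relative to height. Two mothers of the same weight and different height can fall in different categories, and a model with weight but no height treats them as equally exposed before pregnancy.

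Two things are at stake. First, if the child's obesity risk depends on the mother's adiposity rather than her stature, variation due to height dilutes the pre-pregnancy coefficient. That matters because the objective is a comparison across three periods, and this concern applies to only one of the three terms. Second, the overweight/obese pattern in section 2.0 has no explicit analysis. The optional categorisation in section 5.1 concerns weight change, and the joint-model and functional-analysis options there also refer to weight.

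**Working it through.** **The text.** Maternal height has one stated role, eligibility. No analysis text uses it. The asthma model's reference to similar covariates and the chart-review wording are both open-ended: neither names height and neither excludes it. The gap is therefore explicit for the Cox model and unresolved elsewhere.

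**One weight, several categories.** BMI = weight / height². The heights and the cut-offs of 25 and 30 kg/m² are assumptions. At 75 kg:

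- height 1.50 m: 75 / 2.25 = 33.3
- height 1.60 m: 75 / 2.56 = 29.3
- height 1.70 m: 75 / 2.89 = 26.0
- height 1.75 m: 75 / 3.0625 = 24.5

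The weight that corresponds to BMI 30 runs from 30 × 2.25 = 67.5 kg at 1.50 m to 30 × 3.0625 = 91.9 kg at 1.75 m.

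**Dilution of the coefficient.** The plan gives no figure to reproduce and no maternal height or BMI distribution, so every input is an assumption:

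- *s*, the SD of log BMI: 0.20–0.25
- *h*, the SD of log height: 0.037–0.046 (about 6.0–7.5 cm at 163 cm: 163 × 0.037 and 163 × 0.046)
- BMI and height independent, and the hazard dependent on log BMI only

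Since log W = log BMI + 2 log H:

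- height share of log-weight variance = 4h² / (s² + 4h²)
- log-weight coefficient ÷ log-BMI coefficient = 1 − share
- correlation of log weight with log BMI, r = √(1 − share)
- an illustrative HR of 1.50 per SD of log BMI becomes 1.50^r per SD of log weight

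For s = 0.20 and h = 0.037: 4h² = 0.005476, and the share is 0.005476 / (0.04 + 0.005476) = 0.120.

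| s | h | Height share | Coefficient ratio | r | HR per SD |
|---|---|---|---|---|---|
| 0.20 | 0.037 | 0.120 | 0.880 | 0.938 | 1.463 |
| 0.20 | 0.046 | 0.175 | 0.825 | 0.908 | 1.445 |
| 0.25 | 0.037 | 0.081 | 0.919 | 0.959 | 1.475 |
| 0.25 | 0.046 | 0.119 | 0.881 | 0.938 | 1.463 |

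**Simulation checks.**

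- Cox models on simulated data (one run of 40,000 per setting, about 13% events) gave coefficient ratios of 0.865, 0.793, 0.917 and 0.876 without height. With log height added, the ratio was 1.00 in all four. The 0.793 is sampling noise: twelve further runs of 20,000 at that setting averaged 0.82, against 0.825 from the formula.
- On the kg and metre scale (assumed medians BMI 26 and 1.63 m), weight alone explained BMI with R² of 0.82–0.92. Weight plus height explained it with R² of 0.99.

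**Classification.** With mean height 162 cm, SD 6–7 cm, median BMI 26.5 and log-BMI SD 0.15–0.25 (again assumed, with a wider BMI range than above), height made up 8–25% of log-weight variance. The best single weight cut-off misclassified about 9–15% of mothers at BMI 25 and 8–11% at BMI 30.

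**The case against.** The strongest reply is that this is a wording matter with a small effect. Every mother must have a height, for which BMI is the natural use, so weight in section 5.1 may be shorthand. Section 2.0 offers overweight/obesity only as one example of patterns to consider and otherwise frames the exposure as weight. A continuous weight term already captures most of the variation in BMI. The intent may well be as suggested, but the text does not state it, and an analyst following section 5.1 literally would fit weight without height.

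The size estimate also rests wholly on outside inputs and treats the pre-pregnancy term alone, not the full three-term adjusted model. Independence of BMI and height matters: the coefficient ratio becomes 0.88–0.97 with a correlation of −0.2 between log BMI and log height, and 0.80–0.90 with +0.1. This stands. The figures are an illustration, and spread within the adjusted race/ethnicity groups could be smaller.

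Two further points stand in part. Once height is in the model, a continuous BMI model adds little, since weight plus height nearly determines BMI. And an added covariate could alter the influence functions that may guide wave 2 sampling, so the change is not entirely free.

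**Conclusion.** The concern holds, limited to the pre-pregnancy term. As written, that term mixes adiposity with stature, and the overweight/obese pattern in section 2.0 has no explicit category analysis. The mixing is partial: under the four main settings the coefficient is 0.825–0.919 of its log-BMI counterpart, and an HR of 1.50 per SD would read as about 1.45–1.48. These values assume the stated spreads, independence of BMI and height, and a hazard driven by BMI alone. The actual effect on this study's hazard ratio cannot be computed from the documents.

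Nothing here shows the primary result to be invalid. The weight-change terms, the wave 1 strata and the main validation target, the "association between maternal weight change during pregnancy and time to childhood obesity", are not in question. This is a gap between objective and analysis that should be closed because closing it is cheap.

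**What to change.** In section 5.1:

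- Keep the three weight terms in one unit, so the periods remain comparable, and add maternal height to the covariates of both the Cox model and the asthma logistic model.
- Add one analysis with pre-pregnancy BMI in place of pre-pregnancy weight, by overweight/obese category with the cut-offs stated. A continuous BMI version is optional. Keep the comparison of the three periods on the weight model.
- If height-scaled weight was already intended, say so.

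Two smaller additions would help: state which height is used when a mother has several, and name maternal height among the chart-review variables.

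The cost is SAP wording, one covariate that eligibility already guarantees, one extra analysis and, if adopted, one more chart-review item per record. The downsides are that errors in recorded height enter the model and that wave 2 influence functions may shift slightly. The wave 1 strata and the target coefficient do not change.

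### The planned analyses make no allowance for children who share a mother, and the one-year weight windows do not exclude weights from an adjacent pregnancy (minor)

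*Combined protocol and SAP*

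**What the plan says.** Section 4.0 (Study Design) sets the unit of inclusion: "All eligible mother-child dyads in the VUMC Mom-Baby Linkage table will be included for study". The criteria in section 2.1 ask for a linked dyad, a minimum maternal age, and certain weights and heights. They do not restrict a mother to one child or one pregnancy, and they do not exclude multiple births. On numbers, section 2.1 says only that "in an earlier dataset, there were 27,390 mother-child pairs with an existing linkage recorded in a Mom-Baby Linkage table". It does not say how many mothers those pairs represent or how far apart their births were.

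Section 5.1 names the analyses. For the primary outcome, "The cumulative probability of childhood obesity according to age will be estimated using Kaplan-Meier methods", and the association of time to obesity with maternal weight trajectories "before, during, and after pregnancy will be examined using Cox regression adjusted for the key covariates listed above". Asthma is analysed by logistic regression. Maximum-likelihood, multiple-imputation and raking versions are considered to handle errors in the data. None of these descriptions mentions siblings, clustering by mother, robust variance, frailty or random effects.

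The trajectory itself is summarised by "weight during the year prior to pregnancy, weight change during pregnancy, and weight change during the year after pregnancy". No rule covers a weight that falls in one of those years but was taken during another pregnancy.

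Two statements come near the issue. Parity is a listed covariate. The plan also says "We anticipate substantial variation in the frequency of measurements across mothers and children", and among possible responses it considers outputation to "equalize the number of measures per individual".

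**The concern.** There are two separate problems.

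**Variance.** Siblings share a mother, a household and much of their exposure. If their outcomes and exposures are positively correlated within mother, a variance that treats dyads as independent is too small. Confidence intervals are then too narrow and tests reject too often.

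**Exposure definition.** When births are closely spaced, the year after one pregnancy can run into the next, and the year before one pregnancy can reach back into the previous one. A weight that is correct as a measurement is then given the wrong meaning. The study objective in section 2.0 separates excess weight that is lost from excess weight that is kept, and a next-pregnancy weight read as retained weight bears on exactly that contrast.

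**Working it through.** The plan states no sample size, event count or design effect, so there is no figure of its own to reproduce.

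**1. When do the windows overlap?** Section 5.1 gives windows of one year (365 days). For pregnancy length I take 273 days for illustration only; section 2.1 uses that number for eligibility ("At least one measure of weight within 273 days prior to birth of the baby"), not to define pregnancy. The next pregnancy starts inside the index postpartum year when

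birth interval − 273 < 365, that is, birth interval < 638 days (about 21 months).

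The same threshold applies in reverse to the next child's pre-pregnancy year. The overlap is 638 − interval:

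- interval 548 days: 638 − 548 = 90 days
- interval 456 days: 638 − 456 = 182 days

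In the postpartum window these are the first days of the next pregnancy, when the gain is modest. In the pre-pregnancy window they are the last days of the earlier pregnancy, when the excess is larger.

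**2. How much could shared mothers matter?** Assume sibling pairs, with s the share of dyads that have a sibling in the data, ρx the within-mother exposure correlation and ρy the within-mother outcome correlation. All three are assumed. Then

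design effect (DE) = 1 + s·ρx·ρy; true size of a 5% test = 2·(1 − Φ(1.96/√DE)).

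| s | ρx | ρy | DE | True size |
|---|---|---|---|---|
| 0.10 | 0.3 | 0.1 | 1.003 | 5.0% |
| 0.20 | 0.3 | 0.3 | 1.018 | 5.2% |
| 0.40 | 0.3 | 0.5 | 1.06 | 5.7% |
| 0.40 | 0.9 | 0.5 | 1.18 | 7.1% |

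A linear-model simulation with 4,000 repeats gave 1.014, 1.035 and 1.159 for the last three rows, with Monte Carlo error of about 2%. It supports the upper end, but it cannot distinguish the 1.018 case from no effect.

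For Kaplan-Meier curves ρx is replaced by 1, so DE = 1 + s·ρy:

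- 1 + 0.10 × 0.1 = 1.01
- 1 + 0.20 × 0.3 = 1.06
- 1 + 0.40 × 0.5 = 1.20

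**3. How much could the windows matter?** Suppose a share p of dyads has a weight that is m kg too high, unrelated to the true value, and the exposure has standard deviation SD. For a single exposure,

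attenuation = 1 − 1/(1 + p(1 − p)m²/SD²).

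All inputs are assumed:

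- Postpartum change: p = 0.01, m = 1, SD = 7 gives 0.02%; p = 0.02, m = 3, SD = 6 gives 0.49%; p = 0.05, m = 5, SD = 5 gives 4.5%. If the other exposures explain 36% of its variance, the last figure becomes 6.9%.
- Pre-pregnancy weight: p = 0.01, m = 5, SD = 20 gives 0.06%; p = 0.02, m = 8, SD = 18 gives 0.39%; p = 0.05, m = 10, SD = 15 gives 2.1%.

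If close spacing is itself related to child obesity, the direction of the error is not known.

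**The case against.** The strongest reply is that no effect has been demonstrated. The documents give no number of mothers, sibling share or birth interval, and they specify no variance estimator, so narrow intervals are a consequence of the usual default and not something the plan asserts. That stands. It limits the claim to what would follow if dyads were treated as independent.

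A second reply points to safeguards already in the plan. Parity adjusts the mean of the outcome; it neither handles correlation between siblings nor removes a misplaced weight. Outputation is a method for clustered data and could be adapted, but it is only considered here, and for repeated measures on one individual.

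Chart review is the more serious safeguard. It reads the whole record, it covers exposures, and its results inform the full-cohort estimate through the error-corrected analyses. A reader might infer that review would simply confirm such a weight as correctly recorded. The documents do not support that, and they do not say that review would reassign the weight either.

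Third, the illustrated design effects are for the full cohort. In the error-corrected versions, part of the variance comes from the validated subsample, where both siblings may seldom be selected. That is fair and suggests a smaller effect there, although targeted sampling could change it.

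Other stronger readings also fail:

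- The figures above might be taken as limits. They are not: twins share the exposure completely (ρx = 1), families of three or more are left out, and correlations below those shown would make the effect negligible.
- The pair count in section 2.1 might be used to turn shares into numbers of affected dyads. It comes from an earlier dataset and precedes the eligibility criteria.
- Weight change during pregnancy, the exposure for which the validation sample is designed, might be thought to be contaminated. That holds directly only if its baseline is taken from the prior-year window, which section 5.1 does not state.

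**Conclusion.** The point holds as a minor one. The text has a real gap in both respects: no allowance for shared mothers in any named analysis, and no exclusion of weights from an adjacent pregnancy. Intervals that treat dyads as independent would tend to be too narrow, and closely spaced births can put weights in the wrong window.

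The size is unknown from the documents and probably small. The design effect of about 1.00-1.18 and true size of about 5.0-7.1% rest on an assumed sibling share of 10-40%, outcome correlation of 0.1-0.5 and exposure correlation of 0.3-0.9. The attenuation figures rest equally on assumed shares and gains. A reader might infer that the primary association is unreliable; nothing in the documents supports that. The case for acting is that the exposure is the study's main interest and the rules are easily stated before analysis.

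**What to change.** In section 5.1, under the proposed analyses and the methods for error in variables:

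- Use variances clustered on mother for the Cox, logistic and Kaplan-Meier analyses. Carry the clustering into the raking and maximum-likelihood versions, and into each imputed data set before pooling.
- Do not use a weight taken during another linked pregnancy as a pre-pregnancy weight, a postpartum weight, or the baseline for weight change during pregnancy. Define the other pregnancy as running from its linked birth date minus estimated gestational age to that birth.
- Report the number of mothers, the number of dyads per mother, and the number of dyads with an overlapping window.
- Add a sensitivity analysis with one child per mother.

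The cost is slightly wider intervals, extra code for each version, and extraction of birth dates and gestational ages for all linked births. Some postpartum weights in closely spaced births become missing or earlier; how to treat them is debatable and can be left to the study team. Pregnancy start will be approximate, since section 5.1 expects dates other than birth dates to contain errors. Unlinked pregnancies and births elsewhere stay undetected.

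The one-child analysis should remain a sensitivity analysis. With sibling pairs and s = 0.10-0.40 it drops s/2, or 5-20% of dyads, and multiplies standard errors by 1/√(1 − s/2), or 1.026-1.118.
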